4.4 Blinding

This is a double-blind study. Volunteers and investigators performing the assessments, scans and data analysis will remain blind to the identity of the treatment from the time of randomization until database lock and unblinding. The randomisation code will be kept confidential and will only be accessible to research team not involved directly in data collection and analysis prior to unblinding. Urgent unblinding of a particular participant would also occur in the case of emergency in the opinion of medically-trained personnel.

4.5 Determination of Sample Size

We will be using the Emotional Test Battery, which is a well validated set of emotional processing tasks that are sensitive to antidepressant effects. On the facial expression recognition task (FERT), one of the main outcome variables is accuracy at recognising fearful facial expressions and this is the variable used for power calculations. Based on data acquired in (Harmer et al., 2004) comparing citalopram to placebo, if we aim for 0.9 power and a 0.05 false positive rate, a suggested total sample size is 38 (G*power) to ensure determination of group level differences at this variable if they exist. As 5HT₄ agonism is less well studied and the dose required of prucalopride for optimal agonism at the receptor is uncertain, we will aim for 25 individuals per group (total sample size of 50).

5. Changes in the Conduct of the Study or Planned Analyses

5.1 Changes in the Conduct of the Study

There were no changes to the planned conduct of the study.

5.2 Changes from the Analyses Planned in the Protocol

Following analysis of previous work in the research group using a single-dose of Prucalopride, we made minor amendments to the protocol in terms of the hierarchy of outcome measures. These changes were updated on clinicaltrials.gov (NCT03572790) and were resubmitted to the local ethics committee.

The planned analyses were amended in light of the unforeseen circumstance that it is not possible within FSL to add functional or structural masks to data that has been through an fmriprep pipeline due to current restrictions. Therefore, we reverted to our lab's existing fMRI analysis method where data is preprocessed using the FSL pipeline. Minor changes were made to analysis methodology to bring this in line with a typical FSL processing method.

There was also an error in the initial version of the SAP. We had planned to use data from Walsh et al 2018 to create a functional mask for the faces data. Unfortunately, this was not possible, as Walsh et al 2018 used a previous version of the faces task, and during an early stage of the analysis, we discovered that the old and new versions of the faces tasks worked very differently from each other. Therefore, we used an alternative method of creating a functional mask across both tasks for consistency, detailed in this SAP.

This amended version of the SAP was uploaded to clinicaltrials.gov (NCT03572790) in December 2020.

In the December 2020 SAP we planned to change all preprocessing to FSL methods due to restrictions with fmriprep preprocessed data in FSL. However, we later identified that it was not possible to use FSL methods to preprocess multiecho data. Therefore, for the resting state (multiecho) data only we reverted to preprocessing methods described in the original version of the SAP. This minor amendment was uploaded in the SAP to clinicaltrials.gov in October 2022.

6. Outcome Variables

6.1 Schedule of Assessments

	Pre-screening	Screening Visit	Scan Visit	Testing Visit
Procedures	Phone	VISIT 1	VISIT 2	VISIT 3
Send/ present PIS	Х	Х		
Eligibility assessment	Х	Х		
Written informed consent		Х		
SCID		Х		
Medical history		Х		
Physical examination		Х		
Sociodemographics		Х		
Baseline mood (BDI, SHAPS),		Х		
personality (EPQ) and cognitive				
(NART) trait measures				
Randomisation		Х		
State and Trait Anxiety Questionnaire		Х	X (BEFORE	X (BEFORE
(State and Trait form of the State-			AND	AND AFTER)
Trait Anxiety Inventory STAIS)			AFTER)	
Positive and Negative Affect		X	X (BEFORE	X (BEFORE
Schedule (PANAS)			AND	AND AFTER)
			AFTER)	
Side effect questionnaire		X	X (BEFORE	X (BEFORE
			AND	AND AFTER)
			AFTER)	
Stress test response (VAS)		Х	X (BEFORE	X (BEFORE
			AND	AND AFTER)
			AFTER)	
Facial Expression Recognition Task				Х
(FERT)				
Probabilistic learning task (PIL)				X
Auditory verbal learning task (AVLT)				X
Categorisation, recognition and recall				X
of emotional words				
Oxford Memory Test (OMT)				X
fMRI – Emotional Faces Task			X	
fMRI – Memory Task			X	
fMRI – Resting State			X	
MRI – ASL			X	
Physiological parameters, eye			X	
tracking				

^{*}To be undertaken after baseline testing;

Abbreviations: PIS = Participant Information Sheet; SCID = Structured Clinical Interview for DSM diagnoses; BDI = Beck Depression Inventory; VAS = Visual Analogue Scale; EPQ = Eysenck Personality Scale; NART = National Adult Reading Test; (f)MRI = (functional) magnet resonance imaging; ASL = Arterial Spin Labelling; OMT = Oxford Memory Test

6.2 Objectives and Endpoints

These outcomes have been pre-registered on clinicaltrials.gov (NCT03572790). Primary outcomes are identified by bold typeface.

Objectives		Outcome measures / endpoints		
_	ate the effects of seven day e administration compared to			
Primary	Recognition of positive and negative facial expressions	Accuracy to recognise computer-based positive and negative facial expressions (anger, disgust, fear, happy, sad, surprise)		
		Misclassifications (number of responses to each facial expression category incorrectly classified as another facial expression category)		
		Reaction time to recognise facial expressions		
	Performance on Auditory Verbal Learning Task (AVLT)	Accuracy on AVLT (number of items correctly recalled across trials)		
		Number of intrusions (words incorrectly recalled) and number of repetitions (words repeated within the same trial)		
		Number of hits and false alarms in the delayed recognition test		
Secondary	Neural response to emotional faces	Blood Oxygen Level Dependent (BOLD) signal in areas including the amygdala, anterior cingulate cortex, and orbitofrontal cortex		
	Neural response to novel vs. repeated scenes	Blood Oxygen Level Dependent (BOLD) signal to scenes that have previously been seen compared to novel scenes in areas including the hippocampus and parahippocampal regions		
	Reward sensitivity as measured by the Probabilistic Instrumental Learning Task (PILT)	Amount won, amount lost, and total monetary amount earned Accuracy (correct or incorrect symbol choice) and proportion of group choosing correct symbol per trial		

Categorisation, recall, and recognition of emotional words on emotional memory	Emotional Categorisation Task (ECAT): accuracy and reaction time to classify positive and negative descriptor words
tasks	Emotional Recall Task (EREC): number of words correctly recalled (hits) and number of words incorrectly recalled (false alarms)
	Emotional Recognition Task (EMEM): accuracy and reaction time to correctly recognise positive and negative words (hits), and number of incorrectly recognised words (false alarms)
Vigilance to fearful and happy faces on the Facial Dot Probe Task (FDOT)	Vigilance scores derived from reaction time
Resting state connectivity	Resting state connectivity (using resting state fMRI) within and between networks including the default mode, salience, executive control, affective and limbic networks, identified via correlations between spontaneous BOLD activity in spatially independent regions while participants are not actively engaged in an experimental task
Relative and global cerebral blood flow	Relative and global cerebral blood flow identified using Arterial Spin Labelling (ASL)
Visual short term memory on the Oxford Memory Test (OMT)	Accuracy: proportion of correct probe selections, absolute error for probe location, proportion of misbinding errors
	Reaction time

7. Statistical Methods

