Work in our group has revealed that short-term treatment with conventional antidepressants such as SSRIs produces positive biases in the processing of emotional information in healthy volunteers (Harmer, Goodwin, & Cowen, 2009). For example, seven days treatment with the SSRI citalopram decreased recognition of negative facial expressions and recall of negative vs positive stimuli (Harmer, Shelley, Cowen, & Goodwin, 2004). There is also evidence showing that antidepressants have early effects on neural activity, acting on limbic-cortical brain regions that are known to be dysregulated in depression (Ma, 2015). Indeed, a key study by Godlewska and colleagues from our group showed that 7-day treatment with citalopram reduced activity in the anterior cingulate, insula, amygdala and thalamus in response to fearful versus happy facial expressions. Importantly, depressed patients with the greatest reduction in neural activity across these areas went on to respond better to SSRI treatment (Godlewska, Browning, Norbury, Cowen, & Harmer, 2016)

Such effects might be important neuropsychological mechanisms in the mediation of clinical antidepressant action and may also be useful as biomarkers to screen for potential antidepressant activity of novel compounds. It is currently unknown whether activating 5-HT4 receptors has similar effects on emotional processing and neural activity. Such findings would be consistent with the animal studies and important further demonstration that 5-HT4 receptor agonism might be a potentially useful avenue for antidepressant drug development. A previous study in our group revealed acute prucalopride administration (1mg) in 40 healthy volunteers potentiated learning and memory, whereby significantly more words were remembered in a test of auditory verbal learning and memory, and fewer false alarms were

made in a delayed emotional recall task relative to placebo. A single dose of prucalopride did not, however, positively bias emotional processing.

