7.2 Data Cleaning

Data cleaning of the behavioural data and fMRI data will be performed prior to unblinding. Cleaning of behavioural data (i.e. accuracy and reaction times) from the emotional processing tasks will be checked to ensure the tasks have been completed appropriately by

a clinical data analyst at P1vital Products. Specifically, trials where participants show unusually low response times (< 200ms) or high response times (> 6000ms) will be excluded. Similarly, participants who show abnormally low accuracy on the emotional tasks will be excluded (<50% correct responses on the FERT and FDOT). Cleaning of behavioural data from the non-emotional cognition tasks will be performed by the research team, coordinated by the Principal Investigator. Extreme outliers will be excluded from each group on a per task basis. The fMRI data cleaning will be performed by the research team, with guidance from BRC Imaging Support. fMRI data will be visually checked for excessive movement and other artefacts such as signal drop out, as well as to ensure all required data files are present. Formal MRI quality assessment will be undertaken using the MRIQC package (https://mrigc.readthedocs.io/en/stable/index.html), with data considered for rejection if falls outside the normal range of values in the derived image quality metrics. Following collection of all data to be analysed, a final data inclusion meeting will be held with the Principal Investigator prior to unblinding. This will review data quality and confirm exclusion of data from specific tasks. Data will be excluded on a per task basis—that is, a participant may have data excluded for one task, but have all other data available for analysis. Analyses of each task will then be performed on all randomised subjects who have data available for that task.

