8.4.2.1 Primary outcomes

Facial Expression Recognition Task (FERT):

As in previous work (Harmer et al., 2004, Harmer et al., 2009), data will be analysed using repeated measures analyses of variance (ANOVAs). Group (prucalopride or placebo) will be the between-subject factor, and emotion (6 levels) will be the within-subject factor.

Auditory Verbal Learning Task (AVLT):

The number of correctly recalled words on the following trials will be calculated: List A immediate recall trials 1-5. A repeated measures ANOVA will be used to examine if there is an effect of prucalopride administration on word recall (between subject factor: group; within-subject factors: List A acquisition trial). Independent samples t-tests will be conducted to test if there is a group difference in the number of words accurately recalled after a short or long delay (List A short and long delay trials respectively, and the number of intrusions (incorrect words not present in list) and repetitions (correct words recalled more than once in the same acquisition trial) across List A acquisition trials. Independent samples t-tests will also be used to compare List B immediate recall and delayed recognition performance (number of hits and false alarms) between the groups.

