Task	Within Subject Factors	Number of Levels	Outcomes Used	Critical Contrasts Tested in the Analyses
FERT	Face Emotion	6 (Fear, anger, happy, surprise, disgust, sad)	% Accuracy Reaction time Misclassifications	Face emotion x treatment group
ECAT	Word Valence	2 (Positive, negative)	Accuracy Reaction time	Word Valence x treatment group
EREC	Word Valence Accuracy	2 (Positive, negative) 2 (Hits, false alarms)	Number of words recalled (correctly and incorrectly)	1. Word valence x treatment group 2. Word valence x accuracy x treatment group
EMEM	Word valence Accuracy	2 (Positive, negative) 2 (Hits, false alarms)	Number of words recognised (correctly and incorrectly) Reaction time	1. Word Valence x treatment group 2. Word valence x accuracy x treatment group
FDOT	Face Emotion Probe Duration	2 (Fearful, happy) 2 (Masked, unmasked)	Vigilance scores derived from reaction time	Face emotion x treatment group

				2. Face emotion x probe duration x treatment group
AVLT	/LT Trial 5 (List A acquisition tria 1-5)		Number of words recalled Number of intrusions Number of repetitions	Trial x treatment group
PILT	Trial type	2 (Win, loss)	1.Proportion of people choosing correct symbol	Trial type x treatment group
ОМТ	Trial 2 (1 probe, 3 probes)		 Proportion of correct probe selections Absolute error for probe location Reaction Time Proportion of misbinding errors 	1.Trial condition x treatment group

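### As worded, the FERT misclassification outcome counts errors by the face shown, so it nearly duplicates accuracy and cannot separate detecting an emotion from readiness to use its label

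*SAP*

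**What the plan says.** SAP 6.2 lists three FERT measures in its Primary block. The first is "Accuracy to recognise computer-based positive and negative facial expressions (anger, disgust, fear, happy, sad, surprise"). The second is "Misclassifications (number of responses to each facial expression category incorrectly classified as another facial expression category"). The third is reaction time.

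SAP 8.4.2.1 gives one model for the task: "Group (prucalopride or placebo) will be the between-subject factor, and emotion (6 levels) will be the within-subject factor". It does not mention misclassifications. In the table of planned ANOVA comparisons that closes 8.4.2.2, the FERT row has a single within-subject factor, face emotion, with levels "6 (Fear, anger, happy, surprise, disgust, sad"). The outcomes listed against it are percentage "Accuracy Reaction time Misclassifications", and the only critical contrast is face emotion by treatment group. Neither document has a factor for the label the participant chose, and neither defines the count in any other way.

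SAP 7.2 adds a cleaning rule: "trials where participants show unusually low response times (< 200ms) or high response times (> 6000ms) will be excluded". The documents do not give the number of FERT trials per emotion, the treatment of unanswered trials, or whether neutral is a face or a response option in this task.

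The Protocol (Synopsis and section 9) names only accuracy and reaction time as primary FERT measures. Misclassifications first appear in the SAP.

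**The concern.** A six-way labelling task yields a table of face shown against label given. Accuracy is its diagonal. Errors summed along each row, by face shown, are what the diagonal leaves over. Errors summed down each column, by label given, are new information: they show which emotion participants tended to report when it was not there. The SAP's wording and ANOVA factor select the row sums.

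This matters because the rationale in SAP 2.1 is that conventional antidepressants such as SSRIs give short-term treatment that "produces positive biases in the processing of emotional information in healthy volunteers". Lower accuracy for fear could mean that fearful faces are detected less well, or that participants say 'fear' less often to any face. Accuracy and its complement cannot separate the two. The SAP does analyse false alarms alongside hits for emotional recall, emotional recognition and AVLT delayed recognition. The FERT, a primary task and the basis of the sample size in SAP 4.5, has no equivalent.

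There is also a reporting risk. Two outcomes in the Primary block would agree almost by construction, and the agreement could be taken for corroboration.

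**Working it through.** The plan states no figure on this point, so there is none to reproduce. The check is algebra, a numerical illustration and a constructed example.

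**Algebra.** For one participant and one emotion, let n be the valid trials, c the correct responses and a = 100c/n the percentage accuracy. If every valid trial is answered, face-shown misclassifications are

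m = n - c = n(1 - a/100).

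If n is the same for every participant and emotion, m is one fixed linear function of a, and every ANOVA F and p is the same for both. If m is instead expressed as a percentage of n, it equals 100 - a whatever n is. Departures from identity therefore come from unequal n or from unanswered trials, not from information about which label was chosen.

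**Numerical illustration.** From the documents: 25 per group, six emotions, group by emotion ANOVA. Assumed, because the documents do not say: 20 or 40 trials per emotion, 0% or 5% of trials excluded, the confusion probabilities, and a drug-group bias of +0.5 logit towards one label. There is one simulated data set per row and no neutral faces. F is for the group by emotion interaction or, in the last column, group by response label. Here r is the correlation of face-shown errors with accuracy.

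| Trials per emotion | Lost trials | Accuracy F (p) | Face-shown errors F (p) | r | Response-label errors F |
|---|---|---|---|---|---|
| 40 | none | 3.652 (0.0033) | 3.652 (0.0033) | -1.000 | 6.05 |
| 20 | none | 2.057 (0.072) | 2.057 (0.072) | -1.000 | 1.66 |
| 40 | 5% excluded | 2.31 (0.045) | 2.29 (0.046) | -0.995 | 3.45 |
| 20 | 5% excluded | 1.40 (0.227) | 1.49 (0.193) | -0.9915 | 3.41 |
| 40 | 10% of errors are omissions, scored wrong but not as misclassifications | 3.652 (0.0033) | 3.735 (0.0028) | -0.978 | not run |

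In versions with neutral added as a seventh face and label, r was again -1.000 without exclusions and -0.991 to -0.993 with 5% excluded. Across the scenarios run, response-label errors correlated only +0.40 to +0.65 with accuracy, so they are a different variable. Single data sets do not show that they are more powerful: at 20 trials with no exclusions their F was the smaller one.

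**Constructed example.** Take 40 faces per emotion with 30 correct on each, so 10 errors per emotion.

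- Participant A spreads errors evenly: 2 to each of the five other labels.
- Participant B gives one label for every error, except that the 10 errors on that label's own faces go to another single label.

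Counted by face shown, both score 10, 10, 10, 10, 10, 10. Counted by label given, A scores 5 x 2 = 10 on every label, and B scores 10, 0, 50, 0, 0, 0. With 5 x 40 = 200 faces of other categories per label, B's favoured label has a false-label rate of 50/200 = 25%, against 10/200 = 5% for A. The planned outcome cannot tell A from B.

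**The case against.** The strongest reply is that the wording is loose rather than wrong. The phrase in SAP 6.2 could be meant as face-by-label confusion counts or label counts. SAP 8.4.2.1 says only "emotion (6 levels) will be the within-subject factor" and refers to previous work. The battery is a third-party product whose scoring rules are not in the documents. This stands as far as intent goes: the sponsor may have the informative count in mind. It does not rescue the text, because the literal wording indexes errors by the face and the FERT row applies a face-emotion factor to all three outcomes.

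Other points stand and limit the finding:

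- A reader might infer that the outcome repeats accuracy exactly. That holds only with equal valid trials and no omissions, and the SAP's response-time exclusions can make valid trials unequal. Near-duplication is what can be claimed.
- A reader might infer that the outcome cannot show a response bias at all. It can: a bias shifts accuracy by emotion and can produce the planned interaction, as in the simulation. What fails is the separation of bias from sensitivity.
- A reader might infer that the SAP meant this outcome to measure response bias. It does not say so. The link is drawn from the positive-bias rationale and from the false-alarm measures in other tasks.
- A reader might expect a missed effect on how neutral faces are labelled. The documents do not mention neutral FERT faces, so nothing can rest on that.
- SAP 6.2 marks primary outcomes in bold, which is not visible in the text available here. Primary status is read from the item's place in the Primary block.
- The sample size rests on fear accuracy and is unaffected. No loss of power or error inflation has been shown.

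**Conclusion.** The point holds in a limited form. On its literal definition and planned ANOVA factor, the FERT misclassification outcome is valid trials minus correct responses. It is identical to accuracy when valid trials are equal and all answered, and nearly so otherwise (|r| about 0.98 to 0.99). Those last figures depend on assumed exclusion and omission rates, trial numbers and confusion probabilities; the algebra does not. The outcome adds essentially nothing to accuracy and cannot distinguish poorer detection of an emotion from less use of its label. The consequence is lost information on the study's own question and a risk of counting one result twice. The validity of the accuracy analysis is not affected.

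**What to change.** In SAP 6.2, define misclassifications as: for each response label, the number (or rate) of faces of all other categories incorrectly given that label. State the denominator after trial exclusions, how unanswered trials are scored, and whether neutral is a stimulus or a response option. In the FERT row of the ANOVA table, give this outcome its own within-subject factor, response label (6 levels), with the contrast response label by treatment group. Read it beside accuracy, since label errors alone also mix sensitivity and bias.

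If face-shown counts really are intended, drop the outcome as redundant and do not present it as separate evidence from accuracy.

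The cost is a wording change and re-tabulation of trial-level responses already collected; SAP 2.3 keeps the raw task data. If the change is made after unblinding, it should be dated and disclosed as such.

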7.1 Overview

The statistical analysis will be conducted on the behavioural, MRI, resting state, and psychometric data after completion of recruitment and data collection. The data will be statistically compared between the two groups (prucalopride and placebo).

